### PROTOCOL TITLE:

Behavioral Economic Strategies to Improve PRO adherence (BEST-PRO)

### IRB NUMBER

852748

### UPCC NUMBER

34923

### NCT NUMBER

NCT06013176

### ABSTRACT

Routine monitoring of patient-reported outcomes (PROs) for patients with advanced solid malignancies is an evidence-based practice that improves symptoms and quality of life, reduces unplanned acute care, and extends overall survival. However, patient-level adherence and clinician-level adoption to PRO monitoring is suboptimal. We will conduct a three-arm randomized pragmatic trial to test the implementation and effectiveness of patient- and nurse-directed strategies to improve engagement in PRO monitoring across in-clinic and remote monitoring settings. Participants will include patients initiating systemic cancer treatment for solid malignancies at participating Implementation Laboratory sites within the Penn Implementation Science Center in Cancer Control. Eligible patients will be randomized independently to: (1) usual practice (i.e., encounter-based PRO administration via patient portal or tablet); (2) encounter-based PRO monitoring with patient reminders and nurse alerts; or (3) remote PRO monitoring with patient reminders and nurse alerts. The primary outcome will be PRO adherence, measured at the patient level as the proportion of expected PRO questionnaires completed per patient over a 3-month follow-up period. Secondary outcomes will include measures of clinical adoption of PROs, and patient health-related quality of life, duration of therapy, acute care utilization, and treatment delay/modification.

### INTRODUCTION

Routine monitoring of patient-reported outcomes (PROs) for patients with advanced solid malignancies is an evidence-based practice that improves symptoms and quality of life, reduces unplanned acute care, and extends overall survival. Still, there is variation in adoption of and adherence to routine PRO monitoring, owing to multilevel barriers to implementation and concerns among clinicians regarding the utility of PROs in actual practice. While high levels of patient adherence to PRO monitoring have been reported in clinical trials, real-world adherence is

suboptimal. Our preliminary research shows that in a large, multi-site rollout of PROs, patient-level adherence was less than 50 percent, with patients from racial and ethnic minority groups even less likely to complete PRO questionnaires and more likely to report uncontrolled symptoms. Moreover, only half of Penn medical oncologists report that routine PRO monitoring is useful in practice. There is critical need to develop, test, and disseminate strategies to improve patient-level PRO adherence to ensure optimal and equitable symptom management, quality of life, and survival for patients with advanced cancer.

Implementation strategies informed by behavioral economics are ideally suited to address this challenge, as it is fundamentally one of clinician and patient behavior change. For PRO monitoring programs to succeed in transforming cancer care, patients must longitudinally complete PRO questionnaires and clinicians must use the resultant patient-reported data in clinical decision-making. Clinician engagement and use of PRO data begets patient engagement, in part by signaling an approved behavior (injunctive norm) to which patients desire to conform. Repeated feedback is important for sustaining other health-promoting behaviors such as medication adherence. In particular, gamification strategies, which harness game design elements and patient heuristics to motivate behavior change, have shown promise. However, little research has harnessed these insights to promote longitudinal PRO adherence.

## **OBJECTIVES:**

- (1) Evaluate the implementation and effectiveness of patient- and nurse-directed strategies across in-clinic and remote monitoring settings, using a three-arm pragmatic cluster RCT.
  - H1a: Nudges to patients and alerts to nurses will improve patient-level PRO completion and clinician-level PRO engagement
  
- (2) Evaluate moderators of implementation effects, using a quantitative evaluation of secondary data from the electronic health record, area-level data via geocoding, and clinician surveys.
  - H2a: The impact of nudges will be moderated by clinician, patient, and outer setting factors.
  - H2b: Baseline PRO adherence rates will differ by race, ethnicity, and socioeconomic status.
  - H2c: The nudge arms will not be significantly differentially effective across subgroups.

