### **Power and Sample Size**

For our primary comparison of patient-level adherence across study arms, we expect to have 80% power to detect a 14.5 percentage point difference in patient-level adherence, assuming baseline adherence rates of 0.50 (SD 0.40) [based on our preliminary data], a two-sided alpha of 0.05, and a mean of approximately 3 opportunities for each patient to complete the survey. Based on prior trends in Beacon plan treatment starts in 2022, this assumes accrual of approximately 100 patients per month for three months totaling approximately n=300 patients. Over the course of the pragmatic trial, enrollment exceeded expectations at both participating sites. As such, the target accrual was updated to total approximately 480 patients.

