### **Aim 2**

We will evaluate for heterogeneity of implementation effects on PRO adherence by including an interaction term between study arm and, separately, patient-level age (dichotomized), sex, race/ethnicity, income, and geographic location. Evidence for effect modification will be judged based on the z-score corresponding to the ratio of hazard ratios (interaction term) using again a two-sided alpha of 0.05 as the threshold for statistical significance.

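### H2c predicts no significant subgroup difference and has no other criterion, but the interaction tests are too imprecise for a null result to support equal effect

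*Combined protocol and SAP*

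**What the plan says.** Under Objectives, item 2, the protocol lists two hypotheses about effect modification. One is "H2a: The impact of nudges will be moderated by clinician, patient, and outer setting factors". The other is "H2c: The nudge arms will not be significantly differentially effective across subgroups". Between them, H2b concerns baseline adherence by race, ethnicity and socioeconomic status. The subgroups meant in H2c are not named.

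The Aim 2 paragraph of the Statistical Analysis section tests heterogeneity "by including an interaction term between study arm and, separately, patient-level age (dichotomized), sex, race/ethnicity, income, and geographic location". The decision rule is a z-score on the interaction term, "using again a two-sided alpha of 0.05 as the threshold for statistical significance". The documents give no margin, no confidence-interval criterion, no power for any interaction, and no statement of how a non-significant interaction will be read.

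Power and Sample Size covers a main effect only: "80% power to detect a 14.5 percentage point difference in patient-level adherence". The Aim 1 analysis text names Arm 2 vs Arm 1 as the comparison used for power.

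**The concern.** H2c claims no difference and is worded in terms of significance, so a non-significant test is the result it predicts. Non-significance supports equal effect only when the test could have detected a difference that matters. This trial was sized for a single two-arm contrast, and a subgroup contrast within it is much less precise.

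Equity is part of the rationale. The Introduction asks for equitable symptom management, and the Background reports lower completion in Black and Hispanic patients and warns of reinforcing disparities. If a null interaction were read as equal benefit, a strategy that widened the gap could be described as equitable.

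The two hypotheses also share tests. Unless the factors are divided between them, one interaction result on a patient factor counts for H2c and against H2a, or the reverse.

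**Working it through.** **Inputs from the documents.** SD 0.40 and a difference of 14.5 points (Power and Sample Size); two-sided alpha 0.05; 1:1:1 allocation (Study Design); target 480, so 160 per arm.

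**Assumed.** The documents give no subgroup share. I take f = 25%, with a range of 15% to 50%, for a two-level factor equally distributed across arms.

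**The plan's own figure.** At the initial 300 patients (100 per arm), SE = 0.40 × √(2/100) = 0.0566 and 0.145/0.0566 = 2.56. Power is Φ(2.56 − 1.96) = 72.7%, not 80%. An SD of 0.145 × √50 / 2.80 = 0.366 would give 80%. The plan mentions "a mean of approximately 3 opportunities for each patient to complete the survey", which might explain a smaller SD, but it states 0.40. At 160 per arm with SD 0.40, SE = 0.0447 and power is 90.0%. This mismatch is a separate matter; I carry 0.366 only as a sensitivity value.

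**Interaction, Arm 2 vs Arm 1, linear adherence scale.** SE = SD × √(2/(n f) + 2/(n(1 − f))). At f = 25% each arm holds 40 and 120 patients:

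- SE = 0.40 × √(2/40 + 2/120) = 0.103
- 95% CI half-width = 1.96 × 0.103 = 20.2 points
- detectable with 80% power = 2.80 × 0.103 = 28.9 points

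**Chance of missing 0.05 when the subgroup gains nothing.** In scenario A the majority gains 14.5 points. At f = 25%, 0.145/0.103 = 1.40, power is 28.9% and the miss rate is 71.1%. In scenario B 14.5 points is the overall average, so the majority gains 14.5/(1 − f). At f = 25% that is 19.3 points, and the miss rate is 53.5%.

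| Share | SE | 95% half-width (points) | Detectable, 80% power (points) | Miss, A | Miss, B |
|---|---|---|---|---|---|
| 15% | 0.125 | 24.5 | 35.1 | 78.8% | 72.5% |
| 25% | 0.103 | 20.2 | 28.9 | 71.1% | 53.5% |
| 50% | 0.089 | 17.5 | 25.1 | 63.2% | 10.0% |

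**Sensitivity at f = 25%.** With SD 0.366 the half-width is 18.5 points, the detectable difference 26.5 points, and the miss rates 66.5% (A) and 46.6% (B). Pooling Arms 2 and 3 against Arm 1 at SD 0.40, which the plan does not propose, gives a half-width of 17.5 points, a detectable difference of 25.1 points, and miss rates of 63.2% and 42.0%.

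**Could equal effect be shown formally?** At f = 50%, the most favourable share, the 90% CI half-width used in a two one-sided tests procedure is 1.645 × 0.0894 = 14.7 points. With SD 0.40, even a margin as wide as the whole 14.5-point sizing difference could not be met.

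**The case against.** The best case for the plan has five parts.

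1. *The Aim 2 rule is for detecting modification.* A reader might infer that the trial will count H2c as confirmed whenever a test misses 0.05. The documents do not say so, nor do they commit to reporting or disseminating such a conclusion. This stands. The defect is that H2c is worded as non-significance and no other criterion is supplied.

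2. *The miss rate depends on the scenario.* A reader might infer that a total lack of benefit in a subgroup would usually go undetected. That holds at every share from 15% to 50% in scenario A. But scenario A at a 25% share implies an overall effect of only 0.75 × 14.5 = 10.9 points, and the sizing text reads more naturally as an overall effect. In scenario B the miss rate falls below one half somewhat above a 25% share. This stands, so both scenarios are reported. The interval width does not depend on the scenario.

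3. *The calculation is not the test as written.* The Aim 2 text says "Evidence for effect modification will be judged based on the z-score corresponding to the ratio of hazard ratios (interaction term"). Adherence is a proportion modelled by linear regression in Aim 1, so a hazard ratio does not fit the outcome. I used the linear scale; the text needs correcting.

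4. *H2a and H2c need not conflict.* A reader might infer an outright contradiction. H2a also covers clinician and outer setting factors, and H2c follows H2b, so its subgroups may mean race, ethnicity and socioeconomic status. The conflict is firm only for patient factors, and only because the subgroups are undefined and no factor is assigned to either hypothesis.

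5. *Underpowered moderator analyses are common.* True, and not an error in itself. The difficulty is stating a no-difference hypothesis and leaving it to such a test.

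**Conclusion.** The concern holds in this form: H2c is a no-difference hypothesis whose only stated criterion is failure to reach 0.05, and the trial is too imprecise for that failure to support equal effect. The result that depends least on assumptions is the precision: about ±20 points (25 to 18 across shares of 15% to 50%), with a detectable difference of about 29 points (35 to 25), roughly twice the 14.5 points used for sizing. The chance of missing a complete absence of benefit in the subgroup is about 71% (79% to 63%) or about 54% (73% to 10%), depending on whether 14.5 points is the majority effect or the overall average.

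These figures assume the subgroup share, a two-level factor, SD 0.40, 160 per arm and the linear scale. The primary analysis is unaffected. What is at stake is whether the equity hypothesis can be answered as written.

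**What to change.** In Objectives, item 2, restate H2c as an estimation aim and name its factors, for example race/ethnicity and income, following H2b. Assign the remaining Aim 2 factors to H2a. H2a also mentions clinician factors, for which no interaction is listed; the team should either add one or drop that part.

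In the Aim 2 analysis:

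- replace the hazard-ratio wording with the between-subgroup difference in effect on the adherence scale;
- report that difference with its 95% CI for each nudge arm vs Arm 1, since H2c refers to both nudge arms;
- state that a non-significant interaction is not evidence of equal effect, and is reported as inconclusive unless the CI excludes differences that the team declared important before analysis.

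The cost is wording only, with no new patients or data. The downside is that, at this sample size, the equity result will probably be reported as inconclusive.

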## **BACKGROUND:**

Routine PRO monitoring is an evidence-based practice that improves patient outcomes. Patients with cancer commonly experience symptoms which go unrecognized by clinical teams up to half of the time. PROs are a powerful tool to bridge this gap, amplifying the patient experience and improving communication between patients and clinicians. Basch et al. conducted a seminal clinical trial in which weekly PRO symptom assessments with care team alerts led to reduced care utilization, improved quality of life, and lengthened overall survival among patients receiving active treatment for advanced solid tumors. Subsequent randomized trials have corroborated the quality of life and survival advantages of PRO monitoring in other cancer populations and practice settings.

Real-world adherence to PRO monitoring is lower than in seminal clinical trials, with potential racial/ethnic disparities. Multilevel barriers to PRO implementation exist at the patient, clinician, practice, and system levels. While patient adherence to PRO monitoring in seminal trials ranged from 70 to 90 percent, real-world adherence is much lower and more variable. Our preliminary research (under review) demonstrates that in a large, multi-site rollout of PRO monitoring, mean patient-level adherence was less than 50 percent. Moreover, compared to non-Hispanic White patients, Black and Hispanic patients were 9% and 4% less likely to complete PRO questionnaires, respectively, but more likely to report more severe symptoms. These results highlight that historically marginalized subgroups may benefit less from current methods of PRO administration, potentially reinforcing existing disparities in symptom management if not remediated.

This will be the first study to apply behavioral economic strategies to align clinicians and patients in achieving sustained patient-level PRO adherence, and addresses limitations of current PRO approaches. Current approaches to PRO collection are limited by: (1) suboptimal clinician engagement, (2) encounter-based assessments which preclude longitudinal monitoring of PROs outside of the clinic, and (3) insufficient automated effectors actively linking reported symptoms with clinical response. This proposal addresses these limitations by employing behavioral strategies directly targeting clinician engagement, utilizing novel electronic remote monitoring methods to maximize real-time PRO capture, and linking these with pathway-driven automated effectors.

## CHARACTERISTICS OF THE STUDY POPULATION:

### 1. ***Target Population and Accrual:***

The target population will include approximately 480 patients with solid malignancies cared for at the following practice sites of the Penn Medicine Abramson Cancer Center (ACC), referred to hereafter as the “Implementation Laboratory”: **Perelman Center for Advanced Medicine (PCAM) and Princeton Health**. In this pragmatic trial, eligible patients will accrue as they initiate a new line of systemic cancer treatment.

### 2. ***Key Eligibility Criteria:***

#### *Key inclusion criteria*

Eligible patients must meet the following criteria:

- Initiate a new line of systemic cancer therapy (ie, intravenous chemotherapy or immunotherapy) at a participating Implementation Lab site

#### *Key exclusion criteria*

Patients will be ineligible for ANY of the following reasons:

- Active enrollment in a therapeutic clinical trial
- Patient opts out of pragmatic research

### 3. ***Subject Recruitment and Screening:***

Subjects will accrue to the study when initiating a new line of systemic cancer therapy (ie, intravenous chemotherapy or immunotherapy). Subject recruitment and screening will occur pragmatically via weekly queries of upcoming Epic/Beacon treatment plans, identifying patients scheduled to initiate a new line of systemic cancer therapy in the following week.

Given the pragmatic nature of this study and its objective to test implementation strategies to promote engagement in an evidence-based practice in routine cancer care, ***we are requesting a waiver of informed consent***. There are several reasons to justify this request. First, we are assessing the impact of implementation strategies delivered to patients through adjustments in existing clinical workflows using the electronic medical record and other patient communication tools. Second, it would not be feasible to consent every patient enrolled in the trial. Third, individual informed consent might impact patient behavior, thereby complicating the study design and interpretation of its findings. Fourth, none of the proposed strategies forces behavior change. No one will be coerced or forced to engage in PRO monitoring; rather, the goal of nudges is to promote evidence-based practices while preserving autonomy and freedom of choice.

### 4. ***Early Withdrawal of Subjects:***

We are requesting a waiver of informed consent, so the option to withdraw early from this study is not applicable.

### 5. ***Vulnerable Populations:***

We will not be targeting children, pregnant women, fetuses, neonates, or prisoners in this research study.

**6. Populations vulnerable to undue influence or coercion:**

We will not be targeting participants who are likely to be vulnerable to undue influence or coercion in this research study.

**STUDY DESIGN:**

**1. Study design:**

This hybrid type 2 study design will simultaneously evaluate implementation and effectiveness outcomes. We will conduct a three-arm randomized pragmatic trial to test the effect of patient reminders and triage nurse alerts, in the context of remote vs encounter-based PRO monitoring, on implementation and effectiveness outcomes. Participants meeting eligibility criteria will be randomized 1:1:1 to:

- (1) usual practice, consisting of encounter-based PRO monitoring;
- (2) encounter-based PRO monitoring plus patient reminders and triage nurse alerts;
- (3) remote PRO monitoring plus patient reminders and triage nurse alerts

Across arms, the administered PRO questionnaire will consist of 13 validated metrics spanning patient-reported symptoms, quality of life, and performance status. **[Appendix 1]** We will employ rapid cycle approaches to optimize implementation strategies prior to conducting the clinical trial.

**2. Study Duration:**

The study duration will be approximately 6 months, including a 3-month accrual period and 3-month follow-up period per participant over which primary outcomes will be ascertained.

**METHODS:**

**1. Study Instruments:**

We do not anticipate the use of study instruments beyond the PRO questionnaire **[Appendix 1]**, which is already administered in routine practice. Any additional study instruments will be submitted to the IRB as a modification prior to use.

**2. Administration of Surveys and/or Process:**

We do not anticipate the use of surveys beyond the PRO questionnaire **[Appendix 1]**, which is already administered in routine practice. Any additional surveys will be submitted to the IRB as a modification prior to use.

**3. Data Management:**

To minimize the risk of breach of data and confidentiality, we will use secure, encrypted servers to host the data and conduct the analysis. The Penn Medicine Academic Computing Services (PMACS) will be the hub for the hardware and database infrastructure that will support the project. The PMACS is a joint effort of the University of Pennsylvania's Abramson Cancer Center, the Cardiovascular Institute, the Department of Pathology, and the Leonard Davis Institute. The PMACS provides a secure computing environment for a large volume of highly sensitive data, including clinical, genetic, socioeconomic, and financial information. PMACS requires all users of data or applications on PMACS servers to complete a PMACS-hosted cybersecurity awareness course annually, which stresses federal data security policies under data use agreements with the university. The curriculum includes Health Insurance Portability and Accountability Act (HIPAA) training and covers secure data transfer, passwords, computer security habits and knowledge of what constitutes misuse or inappropriate use of the server. We will implement multiple, redundant protective measures to guarantee the privacy and security of the participant data. All investigators and research staff with direct access to the identifiable data will be required to undergo annual responsible conduct of research, cybersecurity, and HIPAA certification in accordance with

University of Pennsylvania regulations. Data will be stored, managed, and analyzed on a secure, encrypted server behind the University of Pennsylvania Health System (UPHS) firewall. All study personnel that will use this data are listed on the IRB application and have completed training in HIPAA standards and the CITI human subjects research. Data access will be password protected. Whenever possible, data will be de-identified for analysis.

**4. Subject Follow-up:**

Subjects will be followed for approximately 3 months after enrollment.

**STUDY PROCEDURES:**

**1. Detailed Description:**

Eligible patients will be identified pragmatically using the criteria listed above, and will be independently randomized to study arms using a three-arm design. A description of the three study arms follows:

- (1) Usual practice.** This arm will consist of encounter-based PRO monitoring, in which patients have an opportunity to complete PRO questionnaires via patient portal in advance of clinical encounters or via tablet during clinical encounters. While clinicians will be encouraged to view and discuss PROs with patients during clinical encounters, they will not be prompted to do so in real-time, nor will there be alerts for escalating symptoms.
- (2) Encounter-based PRO monitoring plus patient reminders and triage nurse alerts.** This arm consists of usual practice (described above) plus the addition of patient reminders to complete PRO questionnaires and triage nurse alerts for severe symptoms. Patient reminders will be operationalized through the Epic patient portal. Triage nurse alerts will be routed to Epic symptom management pools in response to a patient reporting moderate or severe symptoms. Patients will have the opportunity to decline or opt-out of triage nurse support. Clinical interventions stemming from triage nurse alerts will be up to the discretion of clinical teams – ie, clinical responses will be neither prescriptive nor mandatory. Notably, the entry point for triage nurse alerts (ie, Epic symptom management pools), as well as resultant clinical responses, are existing standard operating procedures/practices for patients reporting symptoms by phone.
- (3) Remote PRO monitoring plus patient reminders and triage nurse alerts.** This arm will consist of weekly PRO questionnaires administered via the patient portal, de-linked from clinical encounters. Patient reminders and triage nurse alerts will be operationalized as described in Arm (2).

We will use rapid cycle approaches (RCA) to optimize implementation strategies to ensure face validity and maximum effect. We will focus on optimizing content, messaging, and design. RCA procedures will involve design meetings with study team, discussions with administrators and clinicians who are members of our Implementation Lab, as well as piloting of nudges with potential participants to elicit feedback.

